#### 6.7.8.15. TSQM

The TSQM consists of 14 items of which 13 items are made up of 3 specific scales (Effectiveness, Side Effects, and Convenience) and 1 global satisfaction scale (Global Satisfaction). In addition, 1 item (Item 4) questions whether as a result of taking this medication, the subject experienced any side effects at all, which can be answered by yes and no. [Table 8](#), reproduced from ([Atkinson, Sinha et al. 2004](#)), details the individual items in the TSQM.

**Table 8: List of Questions from TSQM**

Item #	TSQM Item
1 a	How satisfied or dissatisfied are you with the ability of the medication to prevent or treat your condition?
2 a	How satisfied or dissatisfied are you with the way the medication relieves your symptoms?
3 a	How satisfied or dissatisfied are you with the amount of time it takes the medication to start working?
4 b	As a result of taking this medication, do you currently experience any side effects at all?
5	How bothersome are the side effects of the medication you take to treat your condition?
6	To what extent do the side effects interfere with your physical health and ability to function (ie, strength, energy levels, etc.)?
7	To what extent do the side effects interfere with your mental function (ie, ability to think clearly, stay awake, etc.)?
8	To what degree have medication side effects affected your overall satisfaction with the medication?
9	How easy or difficult is it to use the medication in its current form?
10	How easy or difficult is it to plan when you will use the medication each time?
11	How convenient or inconvenient is it to take the medication as instructed?
12	Overall, how confident are you that taking this medication is a good thing for you?
13	How certain are you that the good things about your medication outweigh the bad things?
14 a	Taking all things into account, how satisfied or dissatisfied are you with this medication?

Abbreviations: TSQM = Treatment Satisfaction Questionnaire for Medication.

At baseline, TSQM questionnaires were presented to subjects with instructions that they complete the questionnaire based on their usual medications. At all other time points for collection of TSQM, subjects are asked to think about their level of satisfaction or dissatisfaction with the medication they are taking in this clinical trial.

Scale scores are calculated for each scale and are transformed into scores ranging from 0 to 100 (Quintiles IMS 2017). Of note, a score can be computed for a domain only if no more than 1 item is missing from that domain. The calculations specific to each domain are presented in detail below.

**•Global Satisfaction**

$$[(\text{Sum}(\text{Item 12 to Item 14}) - 3) \text{ divided by } 14] * 100$$

○ *If Item 12 or 13 is missing*

$$[(\text{Sum}(\text{the 2 completed items}) - 2) \text{ divided by } 10] * 100$$

○ *If Item 14 is missing*

$$[(\text{Sum}(\text{Item 12 and Item 13})) - 2] \text{ divided by } 8] * 100$$

**•Effectiveness**

$$[(\text{Item 1} + \text{Item 2} + \text{Item 3}) - 3] \text{ divided by } 18] * 100$$

○ *If 1 item is missing*

$$[(\text{Sum}(\text{the 2 completed items})) - 2] \text{ divided by } 12] * 100$$

**•Side Effects**

If Question 4 is answered ‘No’ then score = 100

Else...

$$[(\text{Sum}(\text{Item 5 to Item 8}) - 4) \text{ divided by } 16] * 100$$

○ *If 1 item is missing*

$$[(\text{Sum}(\text{the 3 completed items})) - 3] \text{ divided by } 12] * 100$$

**•Convenience**

$$[(\text{Sum}(\text{Item 9 to Item 11}) - 3) \text{ divided by } 18] * 100$$

○ *If 1 item is missing*

$$[(\text{Sum}(\text{the 2 completed items})) - 2] \text{ divided by } 12] * 100$$

## **6.8. Handling of Missing Data**

### **6.8.1. Missing Effectiveness Endpoints**

For subjects who prematurely discontinue the study, all available data will be included for the key safety and effectiveness analyses. No imputation for missing data will occur.

### **6.8.2. Missing Start and Stop Dates for Prior and Concomitant Medication**

For analysis of medications, a complete date should be established in order to identify whether a medication was taken during the study treatment period or not. For the purpose of handling partially reported start and stop dates for medication the following algorithm will be applied:

- Missing start day, but month and year present:  
If trial medication had been taken in the same month and year as the occurrence of the medication, then the start day of the event/medication will be assigned to the day of first dose of trial medication.  
Otherwise the start day will be set to the first day of the month.
- Missing start day and month, but year present:  
If trial medication had been taken in the same year as the occurrence of the medication, then the start date of the medication will be assigned to the date of first application of trial medication.  
Otherwise the start day and month will be set to 01 January.
- Missing end day, but month and year present:  
The day will be set to the last day of the month.
- Missing end day and month, but year present:  
The end day and month will be set to the date of trial termination.  
However, if trial termination year is greater than the year of the event/medication, then the day and month will be set to 31 December.
- Completely missing start date:  
For HAE medications collected on subject diaries, the date will be set to the corresponding HAE attack date. For all other concomitant medications, a completely missing start date will be set to the treatment start date (if prior to the medication end date) or otherwise will be set to the medication end date.

In subject data listings, start and stop date of medication will be displayed as reported on the eCRF.

### **6.8.3. Missing Start and Stop Dates for Adverse Events**

The same conventions for addressing incomplete dates for prior and concomitant medications will also be used for AEs.

### **6.8.4. Missing Time of First and Last Dose**

In case of missing time for first dose, it will be assumed that baseline pre-dose measures that were to be taken prior to first dose according to the protocol were in fact taken prior to dosing.

In case the time of the last dose is not reported on the diary, time of dose will be assigned as the median dosing time from all prior doses for the subject, as subjects are to dose once per day at approximately the same time each day.

### **6.8.5. Incomplete Date and Time for a Subject-Reported Attack**

For HAE attacks reported with a missing stop date and or time, the following algorithm will be applied:

- Missing start time but start date present:

The start time will be set to 12:00PM.

- Missing start date and time:

The start date will be set to the diary date for which the question was answered “Yes”.  
The start time will be set to 12:00PM

- Missing stop time, but stop date present:

The stop time will be set to 11:59PM

- Missing stop date and time:

The stop date will be set to the attack start date, the stop time will be set to 11:59PM

## **7. STUDY POPULATION**

### **7.1. Subjects Disposition**

Subject disposition will be presented for all subjects. The number of subjects who completed through each study visit and those that discontinued from the study will be provided. The primary reasons for early discontinuation will also be presented by dose. Reasons for exclusion from the safety population will be tabulated. Days on study will be summarized by treatment group.

Subject status at the end of the study will be listed and summarized based on the safety population, showing the number and percentage of subjects with early discontinuation of study treatment and early withdrawal from the study along with reasons for each item. The listings will include whether subjects discontinued from the study drug, whether they withdrew from the study and the reasons for the discontinuation of study drug, along with the date of first and last dose and the date of completion or discontinuation from the study drug and date of study withdrawal. Duration on study treatment and on the study will also be provided.

A consolidated standards of reporting trials (CONSORT) diagram will be created based on the summary tables for the study report. This will include summary tables assessed for eligibility, subjects excluded (not meeting entrance criteria, declining to participate, and other reasons for exclusion), subjects enrolled, subjects allocated to either treatment group, including subjects who did and did not receive intended treatment (with reasons given for not receiving intended treatment), subjects lost to follow-up or discontinuing treatment (with reasons given), and subjects analyzed vs. not analyzed (with reasons given for subjects who are not included in an analysis).

A summary of enrollment by country and investigator site will be provided. Early discontinuation will be summarized by country and investigator site.

Summaries of prior androgen use will be provided by overall duration of prior use, duration of use within 12 months prior to treatment start date, and time since stopping androgen use to treatment start date (latency).

## 7.2. Screen Failures

The number of screen failures and percent of screened subjects who are screen failures will be summarized along with reasons for screen failure on the disposition table. A listing of demographic information for screen failures will be provided.

## 7.3. Protocol Deviations

Protocol deviations will be included in listings and summaries for the CSR. A separate document will detail decision-making guidelines for determining whether a protocol deviation is major or minor. It will also detail a list of categories of protocol deviations.

## 7.4. Demographic and Baseline Characteristics

Demographics, including age, gender, race, ethnicity, childbearing potential, weight, height, and BMI will be summarized using descriptive statistics by treatment group. Time from last BCX7353 dose to baseline will be summarized and listed for subjects who were enrolled in previous clinical trials of BCX7353.

Age (in years) will be reported as the age at consent or assent, as collected in the eCRF.

Body mass index (kg/m^2) will be calculated using the standard formula:

$$\text{BMI (kg/m}^2\text{)} = \frac{\text{Weight (kg)}}{\text{Height (m)}^2}$$

## 7.5. Listing of Subject Inclusion and Exclusion Criteria

Inclusion and exclusion criteria will be listed for each subject.

## 7.6. HAE Medical and Medication History

HAE and HAE medication history will be summarized for the following where possible:

- HAE history
- Past on-demand treatments of HAE
- Current on-demand treatments of HAE
- Past prophylactic treatments of HAE

Past on-demand treatments will include those medications that were taken as needed and discontinued prior to the initiation of study treatment as recorded on the HAE Medication History Page. Past prophylactic treatments will include those medications that were taken as prophylaxis and discontinued prior to the initiation of study treatment as recorded on the HAE Medication History Page. Current on-demand medications will include those that are noted at screening as currently used for on-demand treatment as recorded on the HAE Medication History Page. Summaries will include a grouping of any C1-INH medication as well as displays of individual medications. The C1-INH grouping will include plasma-derived C1-INH replacement (brand names = Cinryze, Berinert, Haegarda), recombinant C1-INH replacement (brand name = Ruconest), icatibant (brand name = Firazyr), Ecallentide (brand name = Kalbitor), fresh frozen plasma, and lanadelumab (brand name = Takhzyro). The summary of androgens will

include androgens (unspecified), oxandrolone, danazol (brand name = Danocrine), and stanozolol.

For subjects who are not rolling over from a previous BCX7353 study, a summary of screening complement 4 (C4) and functional C1 esterase inhibitor (C1-INHf) will be provided in categories showing how subjects met the inclusion criteria confirming diagnosis of Type I or II HAE. Confirmation by SERPING, if required, will be included in the summary. Categories for C4 will be  $C4 < \text{lower limit of normal (LLN)}$  and  $C4 \geq \text{LLN}$  and for C1-INHf will be  $< 50\%$ ,  $50\%$  to  $< 74\%$ , and  $\geq 74\%$ . Where the C4 test has been repeated, the test result for the repeat will be used in this summary.

In addition, detailed SERPING data will be listed.

### **7.7. Prior and Concomitant Non-HAE and HAE Medications**

Medication use is collected for the period from 30 days prior to Screening to study completion, with the exception of contraceptives, which are collected from 60 days prior to Screening. Medications received and stopped prior to the date of first dose will be considered prior medications.

Medications will be considered as concomitant if the start date of the medication is on or after the date of first intake of study drug or if the start date is prior to the first date of study drug but the medication is ongoing during the treatment period in the study. Medications started more than 30 days post discontinuation of study drug will not be considered concomitant medications.

Medication verbatim text will be coded using the WHODD, March 2017. The number and percentages of subjects taking each medication will be summarized by World Health Organization (WHO) preferred name. Multiple uses of the same medication (by preferred name) will be counted once only per subject per study treatment. No inferential statistics will be provided.

HAE-related medications listed in subject diaries as taken for subject-reported attacks will be listed and summarized separately from HAE-related medications identified as concomitant medications. An attack-level summary will also be provided showing the number of attacks for which the various HAE-related medications were taken based on the subject diary and the concomitant medication form (androgens) in the eCRF.

Subjects who enter the study on prophylactic HAE medications will be summarized by treatment group. The time to discontinuation of prophylactic HAE medications will be estimated by the Kaplan-Meier method. Subjects who enter on prophylactic HAE medications and do not discontinue prophylactic medication will be censored at their last assessment.

All medication data will be listed.

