Fifty-nine subjects (26.0%) prematurely discontinued study drug; 57 subjects (25.1%) discontinued study drug before 48 weeks of dosing. The most common reasons for discontinuation of study drug were perceived lack of efficacy (12.3%) and laboratory abnormalities or TEAEs (8.4%). Overall, more subjects treated with BCX7353 110 mg compared to BCX7353 150 mg discontinued study drug due to perceived lack of efficacy; 17 of 100 subjects (17.0%) vs. 11 of 127 subjects (8.7%). Overall, 19 subjects (8.4%) discontinued study drug due to TEAEs; 6 (6.0%) and 13 subjects (10.2%) in the BCX7353 110 and 150 mg

dose groups, respectively. TEAEs leading to discontinuation in > 1 subject were ALT increased (4 subjects [1.8%]), upper abdominal pain (3 subjects [1.3%]), vomiting (2 subjects [0.9%]), AST increased (2 subjects [0.9%]), hepatic enzyme increased (2 subjects [0.9%]), and liver function test (LFT) abnormal (2 subjects [0.9%]).

The majority of subjects (91.0% and 90.6% of subjects in the BCX7353 110 and 150 mg dose groups, respectively) had at least 1 TEAE during the study. There was no effect of dose on the incidence of AEs. Overall, the most frequently reported TEAEs were nasopharyngitis (30.8%), headache (17.6%), abdominal pain (13.2%), and diarrhea (13.2%).

Long term prior androgen use of ≥ 5 years and discontinuation of androgens within 2 weeks of BCX7353 initiation were correlated with a higher subject incidence of liver-related TEAEs, but not other types of TEAEs. Subjects who discontinued androgens in the 2 weeks prior to initiating BCX7353 (n = 40) experienced liver-related TEAEs in the investigations SOC more frequently than subjects who discontinued androgens ≥ 2 weeks before initiating BCX7353 (n = 113) or those subjects who had never used androgens (n = 74). In these groups, ALT increased, 25.0% vs. 2.7% and 1.4%, respectively; AST increased 17.5% vs. 2.7% and 1.4%, respectively; hepatic enzyme increased, 2.5% vs. 0.9% and 0, respectively; LFT abnormal, 5.0% vs. 0 and 0; and transaminase increased, 2.5% vs. 0 and 0.

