The proportion of days with angioedema symptoms was generally similar for both dose groups and declined over time: during Month 1 the median proportion of days with symptoms was 7.1%; during Month 6 the median proportion of days with symptoms was 3.6%; and during Month 12 the median proportion of days with symptoms was 0.0%.

During the first 24 weeks of study, 22 subjects (9.8%) treated with BCX7353 remained attack free, with slightly more subjects in the BCX7353 150 mg group (11.2%) remaining attack free compared with the BCX7353 110 mg dose group (8.0%). During the first 48 weeks of study, 8 subjects (5.0%) treated with BCX7353 remained attack free, with slightly more subjects in the BCX7353 150 mg group (5.8%) remaining attack free compared with the BCX7353 110 mg dose group (3.6%).

A total of 28 of 227 subjects (12.3%) discontinued treatment in the first 48 weeks of the study due to perceived lack of efficacy, with fewer subjects discontinuing treatment in the BCX7353 150 mg dose group compared to the 110 mg dose group (11 [8.7%] vs. 17 [17.0%], respectively). Twenty of the 28 subjects who discontinued study drug due to a perceived lack of efficacy discontinued prior to Week 12. The proportions of subjects who discontinued BCX7353 due to a perceived lack of efficacy was higher for those subjects who had reported either that they had discontinued androgen use < 2 weeks prior to their first dose of BCX7353 (20.0%) or had used androgens for ≥ 10 years (18.2%), compared to subjects who had never used androgens (12.2%). Twelve of the 28 (42.9%) subjects who discontinued BCX7353 due to a perceived lack of efficacy had used androgen therapy for ≥ 10 years before their first dose of BCX7353. Eight of the 28 (28.6%) subjects who discontinued BCX7353 due to a perceived lack of efficacy and had discontinued androgen therapy < 2 weeks before their first dose of BCX7353.

The median duration of an attack was shorter for subjects treated with BCX7353 150 mg vs. 110 mg (median of 17.7 vs. 28.0 hours). This difference was independent of attack location (ie, abdominal-only, peripheral-only, and mixed).

Overall, subjects assessed about 34% of their attacks as negligible or mild in severity with approximately 60% of attacks resulting in no restriction or a slight restriction of daily activities. Overall, approximately 61% of attacks had no or a slight effect on the subject's appearance. There were no notable differences between the dose groups.

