5.4.3. Study Population Rationale

The study will be limited to adults and adolescents ≥ 12 years of age of both sexes. Children <12 years of age will be excluded from participation in BCX7353 clinical trials until the benefit-risk profile in adults and adolescents has been better characterized. Population PK modeling of PK data generated to date indicate that weight is a covariate on the bioavailability of BCX7353. Simulations of exposures by weight at clinically relevant doses indicated that a weight of < 40 kg is associated with exposures considered significantly higher (ie, $> 20\%$) than those generated from an adult of 70 kg at doses to be studied in this protocol. Therefore, participation in the trial will be restricted to subjects who weigh at least 40 kg. At a weight of 40 kg, simulated exposure was well within the efficacious exposures identified in Study BCX7353-203 that were well-tolerated; therefore, it is anticipated that exposure in adolescent subjects will not exceed safe and tolerable exposures in adults.

In the ongoing BCX7353-204 trial, asymptomatic and transient transaminase elevations have occurred almost exclusively in subjects who have recently (ie, < 2 weeks prior to starting BCX7353) discontinued androgens (BCX7353 IB). Currently the physiological and HAE attack changes that may occur with androgen cessation are not well described. Since androgen use (both current and past) is prevalent in the global HAE community, this protocol will provide data to better characterize androgen discontinuation in HAE patients and allow the development of guidance for treaters and patients who wish to switch from androgens to BCX7353. In order to reduce the incidence of transaminase elevations on study, subjects will be required to have last used androgens at least 28 days prior to initiation of BCX7353.

To date, the BCX7353-204 trial has been conducted primarily outside of the US, including many areas where use of long-term prophylaxis for HAE attacks is uncommon. Since use of prophylactic therapy for HAE attacks is prevalent in the US HAE community, this protocol will provide data to allow the development of guidance for treaters and patients who wish to switch from another prophylactic therapy to BCX7353.

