9.7. Concomitant Medications

All subjects in the study must refrain from taking prohibited concomitant medications as outlined in Section [9.7.1](#).

Details of all prior medications (taken within 30 days of screening) and all current concomitant medication use (including herbal supplements), including all medications administered for the treatment of AEs, will be recorded in the source documentation /CRFs.

Subjects whose illness is being treated with C1-INH, tranexamic acid, or lanadelumab prophylaxis regimens are allowed to continue on their regimen; however, the Investigator is encouraged to assess response to BCX7353 therapy and reduce and/or discontinue prophylactic C1-INH, tranexamic acid, or lanadelumab use over time if clinically warranted.

Steady state levels of BCX7353 are reached with daily dosing between 6 and 12 days. Therefore, the following strategies are recommended for subjects who are beginning BCX7353 in place of another method of prophylaxis:

Table 2. Recommended Strategies for Switching to BCX7353 Prophylaxis from Another Therapy

Current Prophylactic Therapy	Timing of BCX7353 Initiation
Androgens (eg, danazol)	Discontinue androgens. Day 1 of BCX7353 dosing may occur a minimum of 28 days after the last dose of androgens. Androgens may be discontinued or tapered in accordance with the usual practice of the Investigator; however, last dose must occur a minimum of 28 days prior to BCX7353 initiation.
Tranexamic acid	Discontinue tranexamic acid dosing 14 days after first dose of BCX7353.
C1-INH (eg, Cinryze, Haegarda)	Discontinue existing C1-INH dosing schedule 14 days after first dose of BCX7353.
Lanadelumab-flyo	Day 1 of BCX7353 dosing to occur on same day as lanadelumab injection. No further dosing of lanadelumab is required after initiating BCX7353.

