10.3.5. End of Study Visit

Subjects who discontinue study drug will return to the clinic 3 weeks (21 ± 3 days) after the date of their last dose for their end of study or withdrawal assessment. Subjects who discontinue study drug must undergo all study-related procedures outlined in [Table 3](#). Subjects who discontinue the study but will continue to receive BCX7353 via another mechanism will have end-of-study assessments performed at their last regularly scheduled visit.

If an AE is ongoing at the end of study visit, additional clinic visit(s) or telephone contact(s) may be warranted (see Section [12.1.2](#)).

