### **6.7.5. Subjects Entering the Study on Prophylactic HAE Medications**

Any subject who took Berinert, Ruconest, Haegarda, or Cinryze (all C1-inhibitors or C1-esterase inhibitors [C1-INH]) on Study Day 1 with regular frequency of administration (eg, once weekly, twice weekly, etc.) or tranexamic acid taken daily and *not* flagged on the concomitant medications eCRF as ‘PRN’ are considered to be on current prophylactic medication.

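### The Kaplan-Meier curve for stopping other prophylaxis is biased upward if read as the chance of switching to BCX7353, by an amount the documents do not fix

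*SAP*

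**What the plan says.** SAP 7.7 reads: "The time to discontinuation of prophylactic HAE medications will be estimated by the Kaplan-Meier method". Its censoring rule is: "Subjects who enter on prophylactic HAE medications and do not discontinue prophylactic medication will be censored at their last assessment". The rule does not depend on why follow-up ended or on whether the subject is still taking BCX7353.

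The group at risk is defined in SAP 6.7.5. Subjects on regularly scheduled C1-INH, or on daily tranexamic acid not marked as-needed, on Study Day 1 "are considered to be on current prophylactic medication". Neither section says how long a stop must last, what happens on restart, or that the subject must be on BCX7353 when the stop occurs.

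Protocol 5.4.3 gives the purpose: the US cohort is to support "guidance for treaters and patients who wish to switch from another prophylactic therapy to BCX7353". Protocol 9.7 lets subjects continue their prophylaxis alongside BCX7353. For those starting BCX7353 in place of it, Table 2 recommends for C1-INH: "Discontinue existing C1-INH dosing schedule 14 days after first dose of BCX7353". It gives the same timing for tranexamic acid.

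**The concern.** A subject who gives up BCX7353 while still on C1-INH can no longer stop C1-INH while on BCX7353. Censoring treats that subject as having the same later chance of doing so as those who remain. For the switching question, giving up BCX7353 is a competing event, not a loss of information.

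A physician or patient using these data would want the chance of ending up on BCX7353 and off other prophylaxis. To judge by its title list, the SAP has no display of that proportion. Table 14.1.4.4 summarises subjects entering on prophylaxis, but its content is not described. Figure 14.1.6.2 shows time to stopping study drug, but is not specified for this group. SAP 8.2 excludes effectiveness subgroups, and SAP 11 drops the comparison by concomitant C1-INH. The Kaplan-Meier curve is therefore the only time-based estimate available for the purpose, and it errs in the drug's favour.

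**Working it through.** **Inputs from the documents**
- Stopping BCX7353: "57 subjects (25.1%) discontinued study drug before 48 weeks of dosing" (Protocol 5.2.2). 57/227 = 25.1%, which reproduces. It covers all treated subjects at both doses, not the prophylaxis subgroup.
- Timing: "Twenty of the 28 subjects who discontinued study drug due to a perceived lack of efficacy discontinued prior to Week 12" (Protocol 5.2.2). 20/28 = 71%.
- Last assessment after stopping BCX7353: "Subjects who discontinue study drug will return to the clinic 3 weeks (21 ± 3 days) after the date of their last dose" (Protocol 10.3.5). Censoring therefore follows within about 3 weeks.

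The documents give no value for the prophylaxis curve, so its Week 48 level is assumed at 30%, 50%, 70% or 90%.

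**Direction.** At each prophylaxis stop, both estimators use the same hazard increment. Kaplan-Meier multiplies it by the probability of not yet having stopped prophylaxis, with BCX7353 exits removed as if non-informative. Aalen-Johansen multiplies it by the probability of having had neither event, which is never larger. So 1−KM cannot fall below the cumulative incidence.

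**Size, constant hazards.** Let h1 be the weekly hazard of stopping prophylaxis, h2 that of stopping BCX7353, and T = 48.
- 1−KM = 1 − exp(−h1·T)
- CIF = h1/(h1+h2) × [1 − exp(−(h1+h2)·T)]

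For 1−KM = 50% and 25.1% stopping BCX7353: h1·T = −ln(0.50) = 0.693 and h2·T = −ln(0.749) = 0.289. CIF = (0.693/0.982) × (1 − 0.50 × 0.749) = 0.706 × 0.6255 = 44.1%, an excess of 5.9 points.

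The early columns put 20/28 of all BCX7353 stops before Week 12, which is 0.251 × 20/28 = 17.9% by Week 12 and 25.1% by Week 48. This applies the lack-of-efficacy timing to every reason for stopping.

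| 1−KM at Week 48 | CIF, 25.1% stop BCX7353 | Excess (points) | Excess if 15% stop | Excess if 40% stop | CIF, early stops (25.1%) | Excess, early stops |
|---|---|---|---|---|---|---|
| 30% | 26.3% | 3.7 | 2.2 | 6.2 | 24.6% | 5.4 |
| 50% | 44.1% | 5.9 | 3.4 | 9.7 | 41.3% | 8.7 |
| 70% | 62.5% | 7.5 | 4.4 | 12.4 | 58.5% | 11.5 |
| 90% | 82.2% | 7.8 | 4.5 | 13.1 | 76.8% | 13.2 |

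**Three-week lag to the last assessment.** Keeping those who left BCX7353 in the risk set for 3 more weeks lowers the 25.1% excesses to 3.3, 5.2, 6.8 and 7.4 points (constant hazards) and 4.9, 8.1, 10.9 and 12.8 points (early stops). Each change is under 1 point.

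**Prophylaxis stops clustered in the first 4 weeks**, with early BCX7353 stops: 1−KM of 50/70/90% gives CIF of 48.6/68.2/88.1%, an excess of 1.4/1.8/1.9 points. With the 3-week lag the excess is 0.1/0.2/0.3 points.

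**Restarts (rate assumed).** With 1−KM of 70% and CIF of 62.5%, a restart rate of 10% or 20% leaves 62.5 × 0.9 = 56.3% or 62.5 × 0.8 = 50.0% with a sustained stop.

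**The case against.** The strongest reply is that SAP 7.7 never claims to estimate successful switching. It sits among the study-population medication summaries, rules out inferential statistics, and names its quantity as time to discontinuation. Switching is not an objective or endpoint in either document. This stands: the bias belongs to the use that Protocol 5.4.3 invites, not to the calculation.

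A reader might also infer that the SAP ignores restarts and fixes the first stop as final. It says neither. It is silent, and a first-stop curve is only the natural reading. The medication summaries count repeated use of a product once per subject, so on that reading a restart would show only in listings.

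A reader might infer a gap as wide as 67% versus 50%: 25 of 100 leave BCX7353 first, then 50 of the remaining 75 stop prophylaxis. The documents do not support that ordering. They place 20 of 227 subjects (8.8%) as stopping BCX7353 before Week 12 and give no timing for the 57 − 28 = 29 who stopped before Week 48 for other reasons. If Table 2 is followed, prophylaxis ends near Day 14. By then a constant hazard gives only 1 − 0.749^(2/48) = 1.2% off BCX7353.

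Three further points stand. Not everyone who stays on C1-INH has failed to switch, since continuing is permitted. The 25.1% also includes recent androgen stoppers, whose lack-of-efficacy discontinuation was 20.0% against 12.2% in never-users, so it may not fit this subgroup. And the SAP lists protocols only to Version 5.0, when enrolment was largely outside the US, so the curve may rest on few subjects.

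None of this supplies the missing proportion.

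**Conclusion.** The concern holds in a limited form. If the curve is read as the chance of switching to BCX7353, it cannot understate that chance. It overstates it whenever subjects give up BCX7353 while still on prophylaxis and others stop prophylaxis later.

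The size is uncertain. It is about 4 to 8 points at Week 48 with 25.1% stopping BCX7353 and constant hazards, about 5 to 13 points if those stops come early, and under about 2 points if prophylaxis stops cluster in the first 4 weeks. In that last case the curve mainly reflects the Table 2 recommendation, and later restarts and BCX7353 exits carry more information. All these figures use a whole-study discontinuation rate and assumed levels of the curve. The subgroup's size, its BCX7353 discontinuation rate and its restart rate are not given.

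The SAP does not misname its estimate, and its handling of restarts is unstated rather than wrong.

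**What to change.** In SAP 7.7, report an Aalen-Johansen cumulative incidence of stopping all other prophylaxis while on BCX7353, in place of or beside the Kaplan-Meier.
- **Competing event:** BCX7353 discontinuation for lack of efficacy, adverse event, or subject or investigator decision.
- **Censored:** administrative exits, namely data cut, commercial availability, and continuing BCX7353 outside the study. Counting these as failures would bias the estimate the other way.
- **Restarts:** state the rule. Also tabulate, among subjects entering on prophylaxis and not administratively censored by that visit, the proportion on BCX7353 and off other prophylaxis at Weeks 12, 24, 48 and 96. Label it as status, not success, because some subjects may stay on both by choice.

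The SAP already provides for medication use to study completion and for reasons for discontinuation, so no new data should be needed. The cost is a revised paragraph, one extra table and a less favourable figure. The rule is best settled before it is applied to the US cohort.
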